a. Self-mutilation: We will assess self-mutilation using the Columbia-Suicide Severity Rating Scale (C-SSRS). The C-SSRS is a scale administered by a trained individual to assess past suicide attempts and severity of suicidality. Questions address suicidal ideation, intensity of ideation, non-suicidal self-injury, and actual suicide attempts. Questions have either yes/no answers or answer choices scored on a severity of 1-5. The scale exhibits a moderate to high internal consistency, with Cronbach's alpha of 0.7, 0.7, and 0.9, respectively for three existing studies.

b. Suicidality: We will also assess suicidality using the C-SSRS (see item a, above).

c. Intimate Partner Violence (IPV): We will assess IPV using the Revised Conflict Tactics Scale (CTS2). The CTS2 is a self-administered questionnaire which measures the extent of partner conflict and negotiation tactics used. A scale of 0 to 7 to rate 78 relationship behaviors based on frequency. The items belong to the following categories: Negotiation, Psychological Aggression, Physical Assault, Sexual Coercion, and Injury. Cronbach's alpha coefficients range from 0.86- 0.95. Those who meet the criteria severe IPV will be excluded. Women who report 1 or higher (i.e., "My partner did this to me one or more times") for any items in the "Severe" subscale of the Physical Assault, Sexual Coercion, and Injury scales will be excluded from the study (these items are bolded and highlighted on the CTS2, enclosed). Examples of "severe" items include "My partner slammed me against a wall" and "My partner beat me up." We will provide appropriate referral sources for additional preventive and clinical services for women who meet criteria for severe IPV at any time during the intervention.

If a participant is determined to be at serious risk for suicidal ideation, suicide attempts, self-mutilation, or severe IPV at any assessment point (clinical screening, baseline, 8 weeks, and 3-month follow-up), or through the Adverse Event Log, weekly contact, wait-list group follow-up (at 3 weeks and 6 weeks after randomization), or text messaging, the therapist will call [name] immediately by telephone. [name] will then call the participant and immediately assess suicide risk. If risk is determined to be present, the following protocol will be implemented depending on level of risk:

(1) Mild risk (e.g. suicidal ideation present without presence of current plan, low intent, presence of hope, no current means).

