6. In Year 2, we will recommence our recruitment efforts to identify and enroll eligible women into the intervention group and the wait-list group. The interviews during the screening process will be audio-recorded. Women who will be screened in Year 2 go through the same process as women who screened in Year 1 for Asian Women Discussion Group and must meet the same eligibility requirements (see Step 2 and Step 3).
7. Our goal is to screen about 400 women in Year 2. Of this number, we expect about 30% (n=120) to meet all eligibility criteria. We will randomly select 96 eligible women and assign 48 to the AWARE intervention group and 48 to the wait-list group.
8. Individual participation in the AWARE intervention group includes:
 - a. Written consent to participate including consent for the audiotaping of each session.
 - b. Completion of a baseline assessment prior to the start of the group sessions.
 - c. Participation in 105-minute group sessions each week (for a total of 8 weeks) with a small group of other participants and a clinician, covering topics including: Safety, Taking Good Care of Yourself, Compassion, Commitment, Creating Meaning, Setting Boundaries in Relationships, Coping with Triggers, Healthy Relationships, Self-Nurturing, and The Life Choices Game
 - d. \$26 payment and \$4 transportation reimbursement for each weekly group session and \$20 payment and \$4 transportation reimbursement for each assessment.
 - e. Completion of a weekly Adverse Events Log and a weekly questionnaire on the AWARE stories.
 - f. Receipt of and response to daily, secure mobile text messages (called “AWARE Stories”) in between each weekly session to reinforce participation and adherence
 - g. Completion of assessments upon the last intervention session
 - h. Completion of outcome assessments in a follow-up visit 3 months after the last intervention session
9. Individual participation in the wait-list group includes:
 - a. Written consent to participate including consent for the audiotaping of each session.
 - b. Completion of a baseline assessment prior to the start of the group sessions.
 - c. Participation in 90-minute group sessions each week (for a total of 8 weeks plus an additional post-intervention meeting) with a small group of other participants and a clinician, covering topics including: Safety, Taking Good Care of Yourself, Compassion, Commitment, Creating Meaning, Setting Boundaries in Relationships,

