(3) Safety analysis (Hypotheses for safety): For the safety measure, participants will be asked to keep a Weekly Adverse Event Log for measuring safety outcomes (including IPV, suicidal ideation, suicide attempts, and self-mutilation). Our hypotheses are: (A) The AWARE group will have statistically significant lower proportions of suicidal ideation, suicide attempt, and self-mutilation at 8 weeks and 3-month follow-up, compared to baseline. (B) There will be no increased frequency of IPV among the AWARE group between the baseline and post intervention. McNemar's tests will be used to test both (A) and (B). Safety outcomes are measured as developments of adverse event outcomes over the course of the study. These include: (1) suicidal ideation, (2) suicide attempts, (3) self-mutilation, (4) and frequency of IPV. We will estimate the proportion of each adverse event at 95% confidence intervals for participants in the intervention group. We will employ McNemar's tests to compare the proportions of each adverse event in the AWARE group at baseline to the ones in the wait-list group. In addition, mixed effects models for adverse event outcomes will be performed, adjusting for baseline characteristics, such as psychiatric diagnosis severity and substances use, to measure the impact of the baseline characteristics on adverse events and also the pattern of change in adverse events from baseline to the post-intervention follow-up.

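### The safety analysis names a weekly log with no described baseline as its measure, yet tests against baseline; source and look-back period need to be fixed, and suicide attempts cannot be tested this way

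*Protocol*

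**What the plan says.** **Protocol G.3, Aim 2, item (3).** The section opens with the measure: "participants will be asked to keep a Weekly Adverse Event Log for measuring safety outcomes (including IPV, suicidal ideation, suicide attempts, and self-mutilation". It defines what is counted: "Safety outcomes are measured as developments of adverse event outcomes over the course of the study". Hypothesis (A) is "The AWARE group will have statistically significant lower proportions of suicidal ideation, suicide attempt, and self-mutilation at 8 weeks and 3-month follow-up, compared to baseline". Hypothesis (B) is "There will be no increased frequency of IPV among the AWARE group between the baseline and post intervention". Both are assigned to McNemar's test. Neither the C-SSRS nor the CTS2 is mentioned here.

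**Protocol F.4, Detailed Procedure, step 8.** For the AWARE arm the baseline assessment is item b. The log is a separate item (e): "Completion of a weekly Adverse Events Log and a weekly questionnaire on the AWARE stories". No log before treatment is described.

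**Protocol E.5.B (Adverse Events), repeated in H.2 and H.3.** The same events are to be evaluated at baseline, 8 weeks and 3 months, with the C-SSRS for suicidality and self-mutilation and the CTS2 for partner violence. The log comes in addition, though here too it is said to measure safety outcomes. On the period covered, the text says only "The C-SSRS is a scale administered by a trained individual to assess past suicide attempts and severity of suicidality".

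**Protocol F.3, criterion (1).** Women with a suicide attempt in the past year, or with active ideation with intent or plan, are excluded.

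**The concern.** McNemar's test needs the same yes/no outcome on the same woman at two times. The measure named in G.3 is a log that, as described, starts with the intervention, and the outcome is defined as something arising after entry. Neither supplies a baseline value. The analysis section therefore asks for a comparison that its own measure cannot provide, while other sections give a different source that could.

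The choice matters because the proportion of women with at least one event grows with the length of the period asked about. A long baseline period against a short follow-up period gives a fall without any change in risk. A short baseline period against a longer follow-up gives a rise. Establishing safety is a stated purpose of this pilot, and its results are meant to inform a larger trial. A significant fall in suicidality within one arm should not depend on an unstated window.

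**Working it through.** The protocol gives no event rates, look-back periods or sample-size calculation, so there is no stated figure to reproduce. What follows is an illustration.

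**Inputs from the protocol**
- 48 women in the AWARE arm (G.1); 15% expected dropout by week 8 (G.3): 48 × 0.85 = 40.8, taken as 41 pairs.
- A further 5% lost by 3 months: 48 × 0.80 = 38.4, taken as 38 pairs.
- Significance level 0.05 (G.3).

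**Assumptions**
- Constant true risk p8 = 10% per 8 weeks (5% as a variant), no treatment effect, independent periods.
- Exact two-sided McNemar test.
- Baseline windows of 52 weeks, 26 weeks, 8 weeks and one month (52/12 = 4.33 weeks).

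**Step 1: smallest significant result.** With all discordant pairs in one direction, p = 2 × 0.5^k. For k = 5, p = 0.0625; for k = 6, p = 0.031. At least six are needed.

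**Step 2: proportion with an event.** For a window of w weeks, P(w) = 1 − (1 − p8)^(w/8). At p8 = 0.10:
- 52 weeks: 1 − 0.9^6.5 = 0.496
- 26 weeks: 1 − 0.9^3.25 = 0.290
- 13 weeks: 1 − 0.9^1.625 = 0.157
- 4.33 weeks: 1 − 0.9^0.542 = 0.055

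**Step 3: discordant probabilities.** Event at baseline only = Pb(1 − Pf); event at follow-up only = (1 − Pb)Pf. For 52 against 8 weeks: 0.496 × 0.90 = 0.446 and 0.504 × 0.10 = 0.050.

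**Step 4: chance of a significant result with no change in risk.** Binomial sum over the number of discordant pairs and their split:

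| Baseline window | Follow-up window | p8 | Pairs | Result |
|---|---|---|---|---|
| 52 weeks | 8 weeks | 10% | 41 | false fall 97% |
| 26 weeks | 8 weeks | 10% | 41 | false fall 48% |
| 52 weeks | 8 weeks | 5% | 41 | false fall 76% |
| one month | 13 weeks | 10% | 41 | false rise 19% |
| one month | 13 weeks | 10% | 38 | false rise 17% |
| 8 weeks | 8 weeks | 10% | 41 | false fall 0.9% |
| 8 weeks | 8 weeks | 5% | 41 | false fall 0.2% |

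With 40 pairs, the first two rows become 97% and 46%.

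**Step 5: risk that persists within women.** Let each woman's 8-week risk follow a beta distribution with mean 10% and assumed intraclass correlation 0.3, 0.5 or 0.7, and average the Step 3 probabilities over it. With 41 pairs, the false fall for 52 against 8 weeks drops to about 75%, 40% and 7%; for 26 against 8 weeks, to about 28%, 12% and 2%. With equal 8-week windows it stays below 1%.

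**Step 6: suicide attempts.** Past-year attempts are excluded, so with a baseline window of up to one year the baseline proportion is zero, apart from any attempt between screening and the baseline visit. A fall from zero is impossible. With a lifetime window, let L be the assumed share of women with an earlier attempt and suppose none attempts during the trial. The test is significant when at least six women have a history: P(X ≥ 6), X ~ Bin(41, L). For L = 10%, 20% and 30% this is 22%, 86% and 99% (21%, 84% and 99% with 40 pairs). The result reflects the entry rule and the window, not the intervention.

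**The case against.** The strongest reply is that a like-for-like baseline is already scheduled. E.5.B, H.2 and H.3 put the C-SSRS and CTS2 at the visits that hypothesis (A) names, and treat the log as an addition. G.3 never says in so many words that the McNemar pairs come from the log. The questionnaires were to be attached to the application and are not at hand, so their recall periods may be equal and settled there. This stands. A reader might infer that the safety outcomes have no baseline value at all, that the plan mixes instruments, or that a fall in suicidality would be pure artefact. The documents support none of these as fact: mixing is one reading of an unclear section, and the size and direction of any artefact depend on windows that the protocol does not state.

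It is also fair that the percentages rest on assumed risks and windows, that independence between periods is the extreme case (Step 5), and that the 52-week illustration cannot apply to attempts, given the entry rule. The exclusions for ideation with intent or plan and for severe partner violence further limit baseline prevalence.

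The reply does not remove the contradiction. The one section that specifies the tests names the log, defines the outcomes as events after entry, and leaves out the two scales. Using the C-SSRS throughout would also not help if its baseline period were longer than its follow-up period. The problem with attempts follows from the protocol's own text under any window.

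**Conclusion.** The point holds as a contradiction within the protocol. G.3 names a measure without a described baseline and requires a baseline comparison, while E.5.B, H.2 and H.3 give another source for the same outcomes; no reference period is stated for any of them. Unequal sources or windows could produce a significant change in either direction with no change in risk. Under the independence assumption the false-fall rate is about 48% to 97% for baseline windows of 26 to 52 weeks at 10% risk per 8 weeks; strong within-woman persistence can bring it below 10%. Equal 8-week windows keep it under 1%. These figures show what could happen, not a bias shown to exist.

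For suicide attempts the conclusion needs no assumed rate. With a baseline window of up to one year, hypothesis (A) cannot be met; with a longer one, a fall is built in. This rests on the exclusion in F.3 being applied as written; F.4 step 3e repeats the criterion without the past-year clause.

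Severity: should be fixed. It is a pilot, a suitable instrument is already scheduled, and the correction is small.

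**What to change.** Amend G.3, Aim 2, item (3):
- Take the paired outcomes for ideation, self-mutilation and partner violence from the C-SSRS and CTS2, with the same items and one equal look-back length at baseline, 8 weeks and 3 months. Eight weeks is one option; anything longer would reach back before treatment at the week-8 visit.
- Drop suicide attempts from the McNemar test against baseline. Report them as incidence during follow-up: number of women and proportion with 95% confidence interval.
- Use the Weekly Adverse Event Log only for descriptive incidence, such as women with an event and woman-weeks observed, and no longer name it as the measure for the outcomes tested against baseline.

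The cost is wording in the protocol and, if needed, the recall period on the forms. No visit, participant or instrument is added. With an 8-week look-back, the visit 3 months (about 13 weeks) after the last session leaves out roughly the first 13 − 8 = 5 post-treatment weeks from the paired test; events reported for those weeks can still be described as incidence.

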- (2) have a current diagnosis of PTSD (As determined by the Clinical Administered PTSD Scale to diagnose PTSD resulting from trauma that occurred in the past 30 days; this structured interview measures the symptoms of PTSD corresponding to DSM–IV criteria)

Women who meet the threshold criteria will be invited to participate in the first step of the study: participation in the Asian Women Discussion group, which consists of 10 psychotherapy sessions and an additional post-intervention meeting. This focus group will provide crucial feedback to help refine the sessions. Because only ten women who meet the eligibility guidelines will be selected: most women will not be selected.

F.3. Exclusion criteria (Indicate if you have different exclusion criteria for different cohorts)

Exclusion criteria. Women who meet any of the following criteria will be ineligible for the study:

- (1) Significant current risk of homicidal or suicidal behavior (deliberate self-injury where there is at least some admitted or inferred intention to die; particularly, participants who have had a suicide attempt within the past year or participants with active suicidal ideation with intent or plan)
- (2) Presence of schizophrenia, schizoaffective, or organic mental disorders using DSM-IV criteria
- (3) Women of mixed race (i.e., those who do not identify as 100% Chinese, Korean, or Vietnamese or a mixture thereof)
- (4) Victims who have experienced natural disasters or other non-violent trauma only (i.e., those who have not been traumatized by physical or sexual violence)
- (5) Women who are currently victims of severe Intimate Partner Violence (IPV) using The Revised Conflict Tactics Scale (CTS2).
- (6) Women who experience worse outcomes than baseline two weeks after the study begins will be withdrawn from the study.

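### Hypothesis (A) tests suicidal ideation only as a proportion by McNemar's test, so a significant fall can coexist with worsening among women whose ideation persists

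*Protocol*

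**What the plan says.** **Hypothesis and test.** Protocol G.3, Data Analysis for Aim 2, item (3) Safety analysis, states hypothesis (A): the AWARE group will have "statistically significant lower proportions of suicidal ideation, suicide attempt, and self-mutilation at 8 weeks and 3-month follow-up", compared with baseline. McNemar's test is named for both safety hypotheses. For estimation, "We will estimate the proportion of each adverse event at 95% confidence intervals for participants in the intervention group". In addition, "mixed effects models for adverse event outcomes will be performed, adjusting for baseline characteristics", with no outcome scale or link given.

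**Instrument.** E.5.B, Adverse Events, item a, assigns suicidality and self-mutilation to the C-SSRS: "Questions address suicidal ideation, intensity of ideation, non-suicidal self-injury, and actual suicide attempts", and "Questions have either yes/no answers or answer choices scored on a severity of 1-5". The same section plans adverse-event evaluation at baseline, 8 weeks and 3-month follow-up. G.3 (3) also names the Weekly Adverse Event Log as a means of measuring the safety outcomes.

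**Who can enter.** F.3, exclusion (1), removes women at significant current risk of homicidal or suicidal behaviour, in particular "participants who have had a suicide attempt within the past year or participants with active suicidal ideation with intent or plan".

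**Use of severity elsewhere.** The E.5.B risk tiers are graded by intent, hope, plan and means. The mildest tier is "suicidal ideation present without presence of current plan, low intent, presence of hope, no current means". In G.3, Evaluation of Pilot RCT Analysis, CAPS is kept continuous so that change in PTSD is captured sensitively, and HIV outcomes are measured for both status and severity.

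**The concern.** For a woman who enters with mild ideation, the safety question is whether it gets worse. The protocol's own risk tiers rest on that gradient, and G.3 describes safety outcomes as developments over the course of the study. Hypothesis (A) asks only whether ideation is present, and McNemar's test uses only women whose status changes. A woman with passive ideation at baseline and a plan at 8 weeks contributes nothing if both visits score as present.

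Remission in some women could therefore give a significant result in favour of (A) while others in the same arm worsen. The pilot's safety findings are meant to inform a larger trial (Section D; I.2), so a statement that ideation fell would carry forward without the other half of the picture. PTSD is analysed on a scale chosen for sensitivity to change; for suicidal ideation no graded outcome is named.

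**Working it through.** The protocol gives no figure to reproduce. G.2 says that no formal sample size calculation is required, and no baseline rate of ideation is stated. The check is of how the planned test behaves.

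**Inputs from the protocol.** AWARE arm 48 (Section D); dropout 15% by 8 weeks and another 5% at 3 months (G.3, Aim 2, item (1)); significance level 0.05 (G.3). Two-sided testing is assumed, since sidedness is not stated for McNemar's test.

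**Expected pairs in the AWARE arm.**
- 8 weeks: 48 × 0.85 = 40.8, about 41.
- 3 months: 48 × 0.80 = 38.4, or 48 × 0.85 × 0.95 = 38.8, so 38 to 39.

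**The test.** Let b be the women who go from present to absent and c those who go from absent to present. When b > c, exact two-sided p = 2 × P(X ≤ c) with X ~ Binomial(b + c, 0.5). Women present at both visits do not enter the formula, whatever their severity.

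- b = 6, c = 0: 2 × 1/2^6 = 0.031
- b = 8, c = 1: 2 × (1 + 9)/2^9 = 0.039
- b = 10, c = 2: 2 × (1 + 12 + 66)/2^12 = 0.039
- b = 12, c = 3: 2 × (1 + 15 + 105 + 455)/2^15 = 0.035

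**Illustration 1 (assumed counts).** Of 41 women, 20 have ideation at baseline; 8 resolve, 12 persist and 1 is new. The proportion falls from 20/41 (49%) to 13/41 (32%), p = 0.039. If 6 of the 12 who persist worsen, that is 6/41 = 15% of the arm. The p-value is the same for any number worsening from 0 to 12.

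**Illustration 2 (range of assumed baseline rates).** Six women resolve, none is new, and every persisting woman worsens. An exact sign test on the graded score is shown for contrast.

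| Ideation at baseline, of 41 | At 8 weeks | McNemar p | Better / worse | Sign test p |
|---|---|---|---|---|
| 12 (29%) | 6 (15%) | 0.031, lower | 6 / 6 | 1.00 |
| 16 (39%) | 10 (24%) | 0.031, lower | 6 / 10 | 0.45 |
| 20 (49%) | 14 (34%) | 0.031, lower | 6 / 14 | 0.12 |
| 24 (59%) | 18 (44%) | 0.031, lower | 6 / 18 | 0.023, towards worse |

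If no persisting woman worsens, the sign test also gives 0.031 for improvement. These are extreme cases, chosen to show that McNemar's test cannot tell the two situations apart.

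**Timing of a between-arm comparison.** The wait-list starts sessions 3 months after AWARE starts (F.4, Overview), at about week 13. AWARE's follow-up is 3 months after its last session (F.4, step 8h), at about week 8 + 13 = 21. By then the wait-list is at or near the end of its own 8 sessions. Eight weeks is the only scheduled visit with an untreated comparator.

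**The case against.** **The cut-point is not defined.** The protocol does not say what level of ideation counts as present, and that detail could sit in a statistical analysis plan. With a higher cut, a move from mild ideation to a plan would be absent-to-present and would count against AWARE. This stands as a condition on the point. It is not a full answer: exclusion (1) names ideation with intent or plan, so a cut at that level would leave a baseline proportion near zero, with little room for the fall that (A) predicts. Any lower cut leaves women above it whose worsening is not counted.

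**The data source is unclear.** The Weekly Adverse Event Log might feed the test instead of the C-SSRS. This stands, and the fix addresses it.

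**The mixed models might use severity.** A reader might infer that every planned suicidality analysis is present-or-absent. The text does not support that. The models fix no scale, so a graded outcome is not ruled out; none is named either. The point is therefore limited to (A), its McNemar tests and the intervals for proportions.

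**Few women may enter with ideation.** A reader might take exclusion (1) to admit everyone without intent, plan or a past-year attempt. Those cases are introduced as particular examples of a broader exclusion for significant current risk, so the pool may be smaller than that. Some milder ideation can still enter.

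**Escalation is caught anyway.** A reader might infer that worsening would go unnoticed. It would not: the E.5.B tiers trigger assessment and response, therapists and the investigator produce weekly written reports (H.2), and attempts and self-mutilation are separate outcomes. The gap is in the reported safety conclusion.

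**Women who worsen may be withdrawn.** F.3 item (6) and H.1 both provide for this. Such women may have no follow-up assessment and so form no pair. That is a second route by which worsening can leave the test, and the illustrations do not include it.

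**Conclusion.** The point holds in limited form. Hypothesis (A) fixes suicidal ideation as a proportion tested by McNemar's test and names no graded C-SSRS outcome, although graded items are collected. If any ideation counts as present, a significant fall (for example 8 resolved against 1 new, p = 0.039) is compatible with any amount of worsening among women whose ideation persists. What can be missed is worsening within ideation in the reported result.

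This rests on three assumptions: a cut-point low enough for ideation to be present at baseline, the C-SSRS as the source, and two-sided exact testing. The counts are illustrative, since the documents give no baseline rate; the insensitivity is a property of the test and does not depend on them. It is a cheap improvement to what (A) can conclude, and does not show that the safety monitoring fails.

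**What to change.** In G.3, Aim 2, item (3):

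1. Keep hypothesis (A), and state that the C-SSRS is its source and what counts as ideation present.
2. Add the number and proportion of women whose C-SSRS ideation severity category rises from baseline, or who have new suicidal behaviour or self-injury. Add a baseline-by-follow-up severity shift table, and read (A) only alongside it.
3. Compare arms, with a 95% interval for the difference in proportion worsening, at 8 weeks only. E.5.B states an 8-week assessment in general terms, but F.4 step 9 does not list one for the wait-list before its sessions. Reconcile the two and confirm that it applies.
4. Report 3-month worsening within arm only.
5. Show women withdrawn for worsening or suicidality (F.3 item (6); H.1) as a separate row, so that they stay in the summary.

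**Cost.** Some extra wording and tables from scores already collected, provided the untreated 8-week wait-list assessment is confirmed; no clinical rule changes. Precision will be low. With about 41 women per arm and an assumed 6/41 worsening in each, the 95% half-width for the difference is 1.96 × √(2 × 0.146 × 0.854 / 41) = 0.15, or about ±15 percentage points. The summary is descriptive and cannot rule out a moderate difference between arms.

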Quantitative data for protocol evaluation and participant psychometric monitoring: We will evaluate participants in the Asian Women Discussion Group by comparing the results of pre-intervention and post-intervention psychometric measures. These comparisons will be used to determine if the current protocol is achieving the intervention's goals of providing benefits to participant's mental and behavioral health.

Data Analysis for Aim 2 (year 2):

(1) Feasibility Analysis of group psychotherapy: We conservatively anticipate that 15% of participants will dropout during the 8 week RCT. We also anticipate that another 5% will dropout at the 3-month follow-up evaluation. The first stage of analysis will involve estimating the proportion of women who are eligible and agree to enroll in the study. A 95% confidence interval for the proportion will also be produced. Then, among those who enroll, baseline characteristics will be compared between those randomized to the intervention and those randomized to the wait-list control group to assess balance.

We will estimate the proportion of women who adhere at 8 weeks and 3-month follow-up. Mean proportion of women who attend (at 8 weeks and 3-month follow-up) and 95% confidence intervals will be generated for the total sample and then by groups. We will test the

difference between the participants' adherence rates in the intervention and control group at 8 weeks and 3-month follow-up using a chi-square test. We will then examine bivariate associations between baseline characteristics and attrition (each time point considered separately) using chi-square tests for categorical variables and two sample t tests for continuous variables among all participants. Multivariable associations will be examined using multiple logistic regression models for adherence by group, relating those characteristics that were significant in bivariate analysis to attrition, if sample size permits.

(2) Feasibility Analysis of AWARE Stories (Hypothesis for secure mobile messaging): Higher level of satisfaction and higher utilization of secure text messages are positively associated with group psychotherapy attendance. Ordinal chi-square tests will be used to examine the association between ordinal scale (1-4) of messaging satisfaction and utilization questions and psychotherapy attendance.]

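### The safety hypothesis that IPV does not increase is tested only with McNemar's test of difference, which cannot show the absence of an increase

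*Protocol*

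**What the plan says.** The Safety analysis under Aim 2 in protocol section G.3 sets out two hypotheses. (A) predicts "statistically significant lower proportions of suicidal ideation, suicide attempt, and self-mutilation" in the AWARE group at 8 weeks and 3 months compared with baseline. (B) reads: "There will be no increased frequency of IPV among the AWARE group between the baseline and post intervention". One test is named for both ("McNemar's tests will be used to test both (A) and (B").

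The same paragraph plans two further analyses. One is intervals: "We will estimate the proportion of each adverse event at 95% confidence intervals for participants in the intervention group". The other is mixed effects models for the adverse event outcomes, adjusted for baseline characteristics, which also describe the pattern of change from baseline to follow-up. Neither is linked to a conclusion on (B), and no tolerable increase is stated.

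IPV is measured with the CTS2, described under Adverse Events in E.5.B: "A scale of 0 to 7 to rate 78 relationship behaviors based on frequency". On the period covered, G.3 says: "Safety outcomes are measured as developments of adverse event outcomes over the course of the study".

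Two entry rules matter here. F.3 excludes women with severe current IPV. It also excludes women at significant current suicide risk, and picks out those with an attempt in the past year. Step 3(e)(1) of the Detailed Procedure in F.4, which Step 6 applies to the RCT, repeats the suicide-risk exclusion without the past-year clause.

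**The concern.** (B) claims the absence of an increase. McNemar's test asks whether there is evidence of a change. With few discordant pairs it will usually be non-significant whether or not IPV has risen, so a small sample makes (B) look better supported.

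The test also needs a yes/no outcome, whereas (B) speaks of frequency and the CTS2 is a frequency scale. A woman who reports some IPV at baseline and more of it afterwards is a concordant pair and contributes nothing.

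What is at stake is the reported conclusion. Section D says the safety outcomes will help plan a larger study, and a no-increase statement resting on a non-significant test would go into that planning. Care of individual participants through logs, weekly monitoring and referral does not depend on this test.

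**Working it through.** The protocol gives no power, margin or sample size calculation for the safety hypotheses, so there is no stated figure to reproduce.

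**Inputs from the protocol**
- AWARE arm: 48 (G.1).
- Dropout, from G.3 (1): "We conservatively anticipate that 15% of participants will dropout during the 8 week RCT" and "We also anticipate that another 5% will dropout at the 3-month follow-up evaluation". This leaves 48 × 0.85 = 40.8, about 41 pairs at 8 weeks, and 48 × 0.80 = 38.4, about 38 pairs at 3 months.
- Baseline IPV: 9.2%, the less severe rate cited in F.3. F.3 also expects about 10% of subjects to have current IPV.
- Significance level: 0.05 (G.3).

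**Assumptions of mine**
- IPV is reduced to yes/no.
- A share π of 50%, 80% or 100% of baseline cases persists.
- Testing is two-sided (G.3 says two-tailed only for the t-tests).
- The true post-intervention rate is double the baseline, 18.4%.

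**Chance of detecting a true doubling**

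The probability of a new case is 0.184 − 0.092π and of a resolved case 0.092(1 − π). For π = 0.5, 0.8 and 1.0 these are 0.138 and 0.046, 0.110 and 0.018, and 0.092 and 0. I enumerated all outcomes and counted significant increases only.

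| Pairs | Version | π = 0.5 | π = 0.8 | π = 1.0 |
|---|---|---|---|---|
| 41 | exact | 0.156 | 0.174 | 0.171 |
| 41 | continuity-corrected | 0.156 | 0.174 | 0.171 |
| 41 | uncorrected | 0.258 | 0.383 | 0.528 |
| 38 | exact | 0.136 | 0.142 | 0.132 |
| 38 | uncorrected | 0.243 | 0.355 | 0.468 |

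One-sided testing at 41 pairs raises these to 24-32% (exact) and 40-74% (uncorrected). Starting from 10% and doubling to 20%, with 0-50% of baseline cases resolving, two-sided power at 41 pairs is 18-22% (exact) and 28-60% (uncorrected).

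**Worked case: an observed doubling, 4/41 to 8/41, with b = 5 new and c = 1 resolved**
- Exact: 2 × P(X ≤ 1), X ~ Bin(6, ½) = 2 × 7/64 = 0.22.
- Continuity-corrected: (|5 − 1| − 1)²/6 = 1.5, p = 0.22.
- Uncorrected: (5 − 1)²/6 = 2.67, p = 0.10.
- Change: (5 − 1)/41 = +9.8 points. Wald standard error: √(6 − 4²/41)/41 = 0.0578. The 95% interval is 9.8 ± 1.96 × 5.78 = −1.6 to +21.1 points. Newcombe without correction gives −2.1 to +22.7 and Tango −2.6 to +23.7.

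The two-sided test is non-significant in all three versions, while the interval runs to an increase of more than 20 points.

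**Dependence on the version.** Five new and none resolved gives p = 0.0625 (exact), 0.074 (corrected) or 0.025 (uncorrected).

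**What the planned single-proportion intervals give.** Clopper-Pearson limits are 2.7-23.1% for 4/41 and 8.8-34.9% for 8/41. They overlap and ignore the pairing, so they do not describe the change.

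**Suicide attempts in (A).** With no new attempts at follow-up, a significant two-sided fall needs at least 6 of 41 women (14.6%) with a baseline attempt by the exact (p = 0.031) or corrected (p = 0.041) test, or 4 of 41 (9.8%) uncorrected (p = 0.046). One-sided exact needs 5 of 41 (p = 0.031). If the baseline look-back is a year or less, the F.3 exclusion puts the baseline at or near zero and these counts are out of reach. If the look-back is longer than the follow-up window, the proportion falls without any effect of AWARE.

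**The case against.** Several points on the other side have force.

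- **A decision rule.** A reader might infer that the protocol commits to treating non-significance as proof of no increase. It does not say so. What stands is that the only test named for (B) offers no other route to a verdict.
- **Other analyses.** A reader might infer that nothing planned estimates change. The mixed models do describe the pattern of change, and if frequency of IPV is modelled they could capture a worsening in women already positive. What is missing is a link from them to (B).
- **SAP detail.** The version of the test and the yes/no cut are often left to an SAP, and their absence is not the complaint. The pairing of a no-increase hypothesis with a difference test is stated in the protocol itself.
- **Pilot status.** G.2 declares a pilot without a formal sample size calculation, so low power is not in itself an error. It matters because here low power favours the hypothesis.
- **The IPV concern in F.3.** A reader might take it as an acknowledged risk in the enrolled women. It refers to women with severe current IPV, who are excluded, and the same sentence cites an earlier Project FIO finding of no increase. It does not support that reading.
- **Sidedness.** The two-sided figures are my assumption. One-sided, the worked case gives p = 0.051 uncorrected and power is higher, though the exact test still misses a doubling in most trials.
- **Suicide attempts.** The C-SSRS look-back is not given in the text and may be on the attached instrument, so this part is conditional. A reader might infer that all of (A) is untestable. The past-year attempt clause does not touch ideation or self-mutilation.

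**Conclusion.** The point holds for (B). A no-increase hypothesis is assigned a test of difference, without a margin or rule, so a non-significant result could be reported as support even after an observed doubling. Under the stated assumptions (41 pairs, 9.2% baseline, 50-100% persistence, two-sided 0.05) a true doubling would be missed in roughly 83-84% of trials with the exact or corrected test and 47-74% with the uncorrected test. The exact figures move with sidedness, baseline rate and persistence; the mismatch between hypothesis and test does not.

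The suicide-attempt point is secondary and depends on the look-back: a baseline window of a year or less leaves almost nothing to fall from, and one longer than the follow-up window produces a fall by construction. The difference in exclusion wording between F.3 and F.4 Step 3(e)(1) is a minor matter of reconciliation.

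**What to change.** In G.3:

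1. Replace the McNemar verdict on (B) with the paired change in IPV within AWARE and its 95% interval by a named paired method, and state how CTS2 responses are reduced to yes/no. The method matters. With 4/41 at baseline, 1 new and 1 resolved case give an upper limit from +6.8 (Wald) to +10.6 points (Tango), so whether a doubling (+9.2 points) is excluded depends on the choice.
2. Report the change in CTS2 frequency score as well, for example from the mixed model already planned.
3. Treat (B) as descriptive and state the largest increase not excluded. Claim no increase only if the upper limit lies below a margin stated in advance.
4. Add the AWARE-minus-wait-list difference at week 8 with a 95% interval if the wait-list completes the CTS2 then. Week 8 precedes wait-list treatment; the AWARE 3-month visit does not. The Adverse Events text implies assessments at 8 weeks, but the wait-list's own list in F.4 Step 9 does not show a concurrent one, so this needs confirming.
5. Report suicide attempts as counts by arm with exact 95% intervals instead of testing for a fall from baseline.
6. Reconcile the suicide-exclusion wording in F.3 and F.4 Step 3(e)(1).

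Items 1-3, 5 and 6 are changes of wording and analysis. Item 4 costs an extra wait-list assessment only if none is already planned at week 8. The price is candour: the pilot will probably have to say that a moderate rise in IPV is not excluded. Even 2 new and 2 resolved cases among 41 leave an upper limit of about +10 to +12 points.
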